### **5.9. Brain Magnetic Resonance Imaging (CARDIA Brain MRI Substudy)**

Epidemiological studies have established strong relationships between cerebrovascular disease, morphologic brain changes (infarcts, small vessel ischemic lesions, and atrophy) and cognitive decline and dementia. In numerous large studies of cerebrovascular disease, MRI has been shown to provide a safe, non-invasive examination of brain morphology and pathology. They have documented the extent of, and consequences from small vessel ischemic disease (SVID), which primarily reflects small vessel pathology secondary to age, hypertension, and other etiologies of small vessel disease such as DM. While the general relationships between cerebrovascular disease, cerebral ischemic lesions, and functional/cognitive impairment are known, details are lacking, particularly those related to the initial disease. Previous studies based on older imaging technology were relatively insensitive to subtle changes of early disease. In ARIC, CHS, Framingham, and Age Gene/Environment Susceptibility-Reykjavik Study (AGES-RS), most participants were over 60 years old at initial imaging, past the age when the earliest expressions of cerebrovascular disease are reflected by MRI. Previous studies also lack early physical, functional and risk factor measures that are needed to document early disease associations. CARDIA offers the opportunity to look more closely at the earliest stages of disease and its known and possible unknown predictors. This is a critical stage of this debilitating process since there is no treatment to reverse vascular brain insults.

New MRI technology now allows more sensitive and specific evaluations. With higher field strength magnets and advanced radiofrequency technology it is now possible to examine the brain at 1 mm isotropic spatial resolution, approximately an order of magnitude better spatial resolution than previous studies. This allows the focused study of specific brain regions that may show early disease-related changes. Newer pulse sequences such as FLAIR provide greater sensitivity to SVID. Furthermore, this greater spatial resolution and disease sensitivity will be very important for the younger age group in CARDIA.

Importantly, new physiological and functional magnetic resonance (MR) methods, particularly arterial spin labeling (ASL) and BOLD (Blood Oxygen Level Dependent), non-invasively measure regional cerebral blood flow (CBF), vascular reactivity and brain connectivity. This offers CARDIA the opportunity to evaluate not just morphology as in all previous studies, but to directly evaluate cerebrovascular function as well as changes in CBF in response to a physiological task or stress. Critical hypotheses about blood flow and the morphologic and functional consequences will be addressed on a population basis for the first time. Hence this proposed CARDIA Brain MRI Substudy is a novel, detailed investigation of the earliest morphologic and physiologic phases of this disease process. This information could prove critical in prevention and early management of cerebrovascular disease, before irreversible damage and functional consequences.

A defined subset of 719 CARDIA participants at three field centers (Birmingham, Minneapolis, and Oakland) will be re-imaged with brain MRI on designated 3T MR scanner facilities. In the event a participant cannot or will not participate in the follow-up MRI, a replacement will be identified in the non-MRI sub-cohort. All reasonable attempts will be made to ensure the new participant is from the same sex-race group as the participant from the original sample. If matching is not possible then a new participant should be identified on a rolling basis.

The Brain MRI Substudy protocol takes 45-50 minutes per participant and includes 1.0 mm isotropic 3D FLAIR, PD, T2, and T1 weighted images, a 2D axial resting ASL blood flow sequence, diffusion tensor imaging sequence (DTI-30 direction), and breath-hold and resting state BOLD sequences to evaluate vascular reactivity and brain connectivity.

In addition to improved scanning capabilities, new computerized image analytical techniques allow more rigorous, quantitative analysis of the improved data. Contemporary, statistically sophisticated voxel-based analysis improves accuracy and precision in defining cerebrovascular disease, perhaps as much as improved MR methods. Ischemic lesions as identified by MRI generally correspond to classical cerebral infarcts plus the more extensive and common leukoaraiosis (ischemic white matter disease, or SVID), now accepted as a non-necrotic, ischemic effect on myelin that is secondary to the effects of aging, hypertension, and other small vessel pathologic processes. Early reports of this vasculopathy depended on anecdotal observations that were quickly superseded by semi-quantitative, human observer scoring systems that are not directly comparable, have limited reproducibility, and restricted dynamic ranges. The CARDIA automated, digital image analysis methodology reflects the evolution to automatic, quantitative computerized digital image analytical techniques that are very reproducible and offer a greater precision and dynamic range than previous scoring systems.

The image analysis methodology uses an expert trained Support Vector Machine (SVM) to classify all brain tissue into either normal or abnormal (ischemic) gray or white matter and assigns the tissue type to all voxels, each of which is assigned to one of 92 anatomic regions of interest (ROIs) of the cerebrum. Ischemic tissue is further classified into necrotic (traditional infarct) vs non-necrotic (i.e., leukoaraiosis) tissue. In addition, CBF is calculated from the ASL sequence for each voxel as will vascular reactivity by resting and breath-hold BOLD imaging. Voxels are assigned to ROIs that are organized in an anatomically hierarchal system that is collapsed into three for this analysis – the

separate volumes of cerebral gray and white matter and basal ganglia (gray and white matter). Abnormal tissue from these ROIs forms the basis for our secondary outcomes (ischemic lesion volume); the sum of the three is the primary outcome (gray, white matter, and total brain volume). CBF and BOLD reactivity will be additional secondary outcomes, reflecting the physiological substrate of cerebrovascular disease.

#### **5.10. Brain Magnetic Resonance Imaging, Transcranial Doppler, and Cognitive & Gait Assessment (Cerebral Small Vessel Disease Study)**

The ancillary study *Cerebral Small Vessel Disease in Motor and Cognitive Decline* (Cerebral Small Vessel Disease Study) (R01 NS085002; [name], PI) adds a brain MRI, Transcranial Doppler, and cognitive & gait assessment to the Y30 Exam. Below is an excerpt from the Cerebral Small Vessel Disease in Motor and Cognitive Decline Protocol v2; for the entire document, contact [name] at [[contact]](mailto:[contact]).

**OBJECTIVES.** Cerebrovascular disease is an important cause of mobility disability and dementia. Intracranial small vessel disease (SVD) rather than large strategic cortical lesions appear to be the major factor in the clinical expression of age related motor and cognitive decline. Brain parenchymal changes such as cerebral white matter hyperintensities (WMH), lacunar strokes and cerebral microbleeds have been identified as the surrogate radiographic manifestations of SVD. However, current evidence suggests that once established, radiographic SVD is irreversible. Therefore, any treatment has to be directed at the vascular changes that precede radiographic SVD. Yet, very few studies have examined pre-clinical cerebral vascular measures and their relationship to clinical and radiographic outcomes of cerebral SVD.

This study is designed to identify vascular biomarkers of cerebral SVD (measured by Transcranial Doppler ultrasound (TCD): vasoreactivity [VR], dynamic cerebral autoregulation [dCA], neurovascular coupling [NVC], and pulsatility index [PI]) across the SVD spectrum in a high risk population. Specifically, we will examine the central hypothesis that functional changes in cerebral small vessels (measured by TCD) are strongly linked with radiographic SVD in high risk individuals.

Our specific aims are as follow:

**Aim 1:** Test the hypothesis that vascular biomarkers measured by TCD are associated with mobility and cognition in individuals with vascular risk factors.

**Aim 2:** Test the hypothesis that vascular biomarkers measured by TCD are associated with radiographic SVD in individuals with vascular risk factors.

**Aim 3:** Test the hypothesis that vascular biomarkers (TCD measures) mediate the relationship between vascular risk and radiographic SVD in high risk individuals.

**BACKGROUND.** The global population is aging. In 2010, 13% of the US population was over the age 65 and by 2020 this number is projected to increase to 16%, translating to 54 million older adults living in the US (US census Bureau, 2010). Cognitive and mobility impairments are the two most common causes of disability in older adults. These two geriatric disorders can lead to disabling forms of dementia and falls. Therefore, to effectively prevent these conditions, we need to identify individuals at risk in the pre-clinical state.

Evidence from epidemiological and clinico-pathological studies has established a strong link between vascular disease and age related clinical outcomes of cognitive and gait impairment. Slow gait speed has been strongly associated with increased blood pressure, increased risk of cardiovascular death, and an increase in incident ischemic stroke risk. Vascular contribution to cognitive impairment and

dementia has been well established in a number of prior studies and summarized in a recent statement from the American Heart Association. Moreover, various brain structural changes attributed to cerebral small vessel disease and measured by magnetic resonance imaging (MRI) have been associated with disorders of cognition, gait, and falls. These MRI changes which include white matter hyperintensities (WMH), lacunar strokes, and cerebral microbleeds (CMB) have become accepted as surrogate measures of cerebral small vessel disease (for detailed review see). Therefore, vascular contributions to mobility and cognitive impairment are significant, yet we know very little about the pre-clinical vascular changes which lead to radiographic small vessel disease (SVD) and the associated clinical outcomes.

Among the vascular pathologies affecting the aging human brain, cerebral SVD is the most common degenerative vascular disorder, much more frequent than cerebral macrovascular disease (for detailed review see). While we have made significant radiological advances in imaging the brain structure and its large vessels, our ability to image or to functionally assess the small vessels of the brain has been limited. Recent studies have shown that measures of peripheral large vessel disease such as aortic pulse wave velocity and carotid intima media thickness and stiffness are both associated with surrogate MRI measures of small vessel disease, gait speed and cognitive function (for detailed review see). These studies have led to the hypothesis that increased central arterial stiffness exposes the cerebral small vessels to abnormal flow pulsations and contributes to the pathogenesis of cerebral SVD. However, because none of these studies actually measured cerebral small vessel function, we know very little about cerebral small vessel structure and function in relation to motor and cognitive decline. A few recent studies have started to use TCD to examine the relationship between cerebral small vessel function and MRI changes. These studies have shown that TCD derived pulsatility index and vasoreactivity are cross-sectionally associated with WMH. Very few studies, all limited to cross-sectional analyses, have also examined the relationship between cerebral small vessel TCD measures and cognitive and mobility impairment. We have shown that cerebral vasoreactivity and neurovascular coupling are both associated with gait speed in an elderly cohort. A few studies have also shown impaired vasoreactivity in patients with carotid stenosis. Only one study using positron emission tomography (PET) in 27 hypertensive participants has shown reduced cerebral blood flow 3 years prior to the onset of cognitive decline. There are no data from population based longitudinal studies linking pre-clinical cerebral small vessel function (as measured by TCD; not MRI surrogate measures or peripheral vascular measures) to subsequent cognitive and mobility impairment. To alter the course of cerebral small vessel disease we need a better understanding of the changes affecting these vessels in the preclinical state where interventions would be most effective.

As the tools to measure cerebral small vessel function become increasingly more sophisticated we are now well poised to advance our understanding of the physiological changes underlying cerebral SVD by directly studying cerebral small vessel function. The introduction of transcranial Doppler ultrasound (TCD) to measure cerebral blood flow velocity provided a powerful tool for non-invasive assessment of cerebral vascular responses to various physiological challenges such as motor or cognitive activation, or change in blood pressure and end-tidal carbon dioxide which we know are regulated at the level of arterioles or resistance vessels of the brain. Since the mechanisms underlying each of these vascular responses are likely different, they have been traditionally distinguished by different labels. Changes in cerebral blood flow velocity in response to sudden changes in blood pressure is referred to as dynamic cerebral autoregulation (dCA). Changes in cerebral blood flow velocity in response to changes in end-tidal CO2 is referred to as cerebral vasoreactivity (VR). Changes in cerebral blood flow velocity in response to a motor or cognitive task is referred to as neurovascular coupling (NVC) or functional hyperemia. In addition to these three functional measures, the resting cerebral blood flow velocity waveform can be also used to calculate a pulsatility index (PI) which is a measure of

cerebrovascular compliance. Using these approaches, TCD, which can provide continuous non-invasive beat-to-beat measurement of the cerebral blood flow velocity in the basal cerebral arteries with a high temporal resolution, has become the most commonly utilized tool to study cerebrovascular function in humans.

In this study, we propose to use TCD to characterize cerebral small vessel function and its relationship to vascular risk factors, radiographic SVD as well as gait and cognitive function across the spectrum of age and vascular risk factors in a cohort of community dwelling individuals agreeable to participate in our study. These study participants will undergo a full TCD assessment, a full cognitive and mobility battery and a brain MRI study. Findings from this study will extend our preliminary work (see below) and help us characterize small vessel function across the spectrum of age and vascular risk factors and understand its relationship with gait and cognition (Aim 1) as well as radiographic small vessel disease (Aim 2), and help us examine possible mechanisms linking vascular risk factors to age related cognitive decline and mobility impairment (Aim 3).

The preliminary data described below establishes the relationship between our TCD measures of small vessel function, cognitive impairment, slow gait and radiographic small vessel disease in an elderly cohort late in the disease when neurological changes are not reversible. In the next phase of our study proposed in this protocol, we want to understand these relationships across age and vascular risk factor spectrum, before significant clinical cognitive and mobility impairment has manifested. This knowledge will allow us to identify pre-clinical vascular measures which would lead to novel diagnostic and therapeutic targets to alleviate the devastating consequences of age related cerebral small vessel disease.

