- Carry at least one of the above diagnoses
- Be able to provide informed consent
- MMSE score greater than or equal to 20

Exclusion Criteria:

- Absence of TCD temporal acoustic windows
- Scores below a 20 on the MMSE at screening
- Significant cardiac disease (such as active angina or symptomatic heart failure)
- COPD
- Anxiety Disorder
- Those who will not pass the standard MRI screening will be excluded from the MRI portion of the study, but will be able to undergo the TCD and clinical assessments.

MRI Exclusion Criteria:

- Claustrophobia
- Any metal implants
- Not able to lie flat for 60 minutes

Inclusion will be limited to adults between 18 and 89 years of age who are capable of providing informed consent. Pregnant women and prisoners will not be included.

**STUDY-WIDE NUMBER OF PARTICIPANTS.** We plan to enroll 250 participants in this research study at Northwestern Medicine.

**STUDY TIMELINES.** We anticipate to enroll the study participants over 3 years and to complete data analysis over a 6 month period once study accrual has been met. The total study time will be 1.5-2 hours for the TCD/cognitive measures and 1 hour for the MRI. The MRI may be done on the same day, or may be scheduled for a second visit. This study will require no additional visits or follow-up.

**PROCEDURES INVOLVED.** This study will involve up to 2 visits and a total participation time of 3 hours. Total study time will be 1.5-2 hours for the TCD/cognitive measures and 1 hour for the MRI. All participants will undergo a detailed medical history as well as a screening MMSE (those scoring below 20 will be excluded from further participation). Enrolled participants will undergo a TCD battery, cognitive assessment, and gait assessment. The MRI may be done on the same day, or may be scheduled for a second visit. This study will require no additional visits or follow-up.

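### Cerebral Small Vessel Disease Study, Aim 3: with one TCD battery, one MRI and no follow-up, the data cannot show that TCD changes come before radiographic SVD, which mediation requires

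*Protocol*

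**What the plan says.** Section 5.10 of the protocol gives three aims. Aims 1 and 2 concern associations of TCD measures with mobility and cognition, and with radiographic SVD. Aim 3 is directional: "Test the hypothesis that vascular biomarkers (TCD measures) mediate the relationship between vascular risk and radiographic SVD in high risk individuals". The Objectives supply the motive, which is that radiographic SVD appears irreversible once established: "Therefore, any treatment has to be directed at the vascular changes that precede radiographic SVD".

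The schedule is under Study Timelines and Procedures Involved. Each participant has one TCD session with cognitive and gait tests, and one MRI: "The MRI may be done on the same day, or may be scheduled for a second visit". Then: "This study will require no additional visits or follow-up". On size: "We plan to enroll 250 participants in this research study at Northwestern Medicine". People who fail MRI screening, or who decline the scan, may still complete the TCD and clinical parts (Exclusion Criteria; Recruitment Methods).

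The list of qualifying diagnoses includes cerebrovascular disease, with small vessel disease named. Recruits come from hospital advertising and from the CARDIA cohort at Northwestern. The CARDIA Brain MRI Substudy (Section 5.9) runs at "three field centers (Birmingham, Minneapolis, and Oakland"), which leaves out Chicago. The Chicago consent forms in Section 4.2 do not include one for that substudy.

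**The concern.** Mediation is a statement about order: risk acts first, TCD function changes next, and radiographic SVD follows. The exposure can be placed first for CARDIA recruits, who bring decades of risk-factor data. Nothing in the design places the mediator before the outcome. TCD and SVD are each observed once, no interval is set in which SVD could develop after the TCD reading, and some participants will have SVD when they enter.

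Lesions that disturb vessel function would also produce correlations of TCD with risk and with SVD, so a mediation test could come out positive when TCD has no effect on SVD. Because the Objectives link the work to treating changes that come before lesions, such a result could be taken as support for TCD function as a treatment target when it is only a marker of existing damage.

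**Working it through.** **Order in time**

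- Risk before TCD and MRI: available for CARDIA recruits from earlier exams. No comparable repeated history is described for those recruited by advertisement.
- TCD before SVD: not available. There is one TCD battery and one MRI, no earlier TCD is described, and no earlier brain MRI is documented for the Northwestern site.
- SVD absent at the time of TCD: not required, since existing small vessel disease is a qualifying diagnosis.
- The protocol's own view: at the end of Preliminary Data it names the cross-sectional analysis, along with small numbers, as a limitation of its pilot findings. The new study is larger but keeps the cross-sectional design.

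**Illustration of size**

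The protocol states no alpha, power, effect size or mediation model for Aim 3, so there is no figure to reproduce. Assumptions: standardised linear variables, two-sided 5% level, mediation declared when both paths are significant (critical value 1.97), order fully reversed (risk to SVD to TCD) and no effect of TCD on SVD. Let r be the risk-SVD path and also the SVD-TCD path.

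- Risk-TCD path: a = r × r
- TCD-SVD path adjusted for risk: b = (r − a·r)/(1 − a²)
- Apparent mediated share: a·b/r
- SE(a) = √[(1 − a²)/(n − 2)]
- SE(b) = √[(1 − R²)/((1 − a²)(n − 3))], where R² is from the regression of SVD on risk and TCD

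For r = 0.4 and n = 250:

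- a = 0.16; b = (0.4 − 0.064)/0.9744 = 0.345; share = 0.16 × 0.345/0.4 = 13.8%
- SE(a) = √(0.9744/248) = 0.0627, so a/SE(a) = 2.55
- The adjusted risk coefficient is also 0.345, so R² = 0.345 × 0.4 + 0.345 × 0.4 = 0.276; SE(b) = 0.0549 and b/SE(b) = 6.29
- Chance that both are significant ≈ Φ(2.55 − 1.97) × 1 ≈ 0.72

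Simulation with 4,000 runs per cell agrees:

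| Both paths | Reversed order called mediation, n = 250 | Same, n = 150 | Median apparent share, n = 250 |
|---|---|---|---|
| 0.2 | 8.5% | 6% | 4% |
| 0.3 | 29% | 19% | 8% |
| 0.4 | 73% | 49% | 14% |
| 0.5 | 98% | 87% | 20% |

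The Sobel test gives 3%, 22%, 69% and 97% at n = 250. When risk causes both TCD change and SVD but the two are otherwise unlinked, the joint test stays near its nominal level (4.6% to 5.4% at n = 250), so the excess comes from the reversed link. True forward mediation with the same paths is declared in 78%, 99%, 100% and 100% of runs.

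Unequal paths behave alike. With risk-SVD 0.4 and SVD-TCD 0.5: a = 0.20, b = (0.5 − 0.08)/0.96 = 0.4375, share = 0.0875/0.4 = 21.9%, Sobel z = 3.0 at n = 250.

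**The case against.** The section is an excerpt of a longer ancillary protocol, and an analysis plan may exist. That covers the choice of test, the covariates and the sensitivity analyses, and their absence here is no fault. It does not cover the aim and the visit schedule, which are fixed in this text. No analysis of one TCD and one MRI recovers their order.

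Mediation can also be meant statistically. Section 5.1.3 describes it for the core study as comparing a difference before and after adjustment. If Aim 3 means only that, the remedy is to say so, because the Objectives tie the aim to changes that come before lesions.

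The illustration is the extreme case of complete reversal, on assumed paths. At paths of 0.2 the false declaration rate is under 9%. Aim 3 also needs the MRI, and people without one may stay in the study, so its sample may be below 250. These points limit the size, and a reader should not infer that reversed causation would always pass the test.

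Three further readings are tempting and not supported:

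- The Background says "This knowledge will allow us to identify pre-clinical vascular measures", which might be taken to mean before MRI lesions. The preceding sentence ties it to the time before marked cognitive and gait impairment appears, so that wording need not go.
- The Background also says "Very few studies, all limited to cross-sectional analyses, have also examined the relationship between cerebral small vessel TCD measures and cognitive and mobility impairment". That remark concerns cognition and mobility, and is not a criticism of earlier work on SVD. The relevant admission is the one about the pilot data.
- Fitting the reversed model might seem to settle direction. With three variables measured once and a direct path allowed, both orders fit equally well.

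**Conclusion.** The point holds for Aim 3. As designed, the study can show whether TCD measures statistically account for the association between vascular risk and radiographic SVD. It cannot show that TCD changes lie on the path to SVD. This follows from the schedule and the entry criteria and needs no assumption about effect size.

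How often a reversed order would be mistaken for mediation does depend on assumptions: about 9% to 98% for equal paths of 0.2 to 0.5 with 250 scanned, and 6% to 87% with 150. Aims 1 and 2 are association aims and are unaffected, as is the core Year 30 exam.

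**What to change.** - Restate Aim 3 as a cross-sectional test of whether TCD measures statistically account for the association between vascular risk and radiographic SVD, and state that it will not support a conclusion that TCD changes come before radiographic SVD.
- For CARDIA recruits, take the exposure from earlier exams (Y0 to Y25), so that risk at least precedes both TCD and MRI.
- Report the risk-TCD association in participants without radiographic SVD as supporting evidence. Visible lesions cannot explain abnormal TCD in that group, although the analysis does not estimate any effect of TCD on SVD.
- Show the reversed-order model beside Aim 3 only to display the ambiguity, and say that it cannot identify direction.

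This takes a change of wording and a few analyses of data already planned, with no added visits. The price is a weaker claim for Aim 3 and a smaller, less precise SVD-free subset.
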